classified as rural or highly rural. Using methods that have been successful in our prior Function QUERI work, and in partnership with the Physical Medicine & Rehabilitation Service and VISN 6, we will invite participation in the Group PT project in national and regional forums, e.g. monthly PM&R and Chiefs of Staff calls. Randomization will be stratified based on the Complexity Level, where sites 1a, 1b, and 1c are one category and all others (2, 3, CBOCs/Health Care Centers) are the other category (bottom quartile vs. higher; MISSION Act Quality Standard) and rurality, where sites serving ≥50% rural/highly rural Veterans are one category and sites serving <50% rural/highly rural Veterans are another category.

Implementation activities. Foundational REP has been described previously. One component of Foundation REP is the data dashboard, which will assist sites with tracking their own data. The FQ team will use CDW data (e.g., # of consults, # of completed evaluations, etc.) to generate a tool to assist sites with quality improvement efforts. Data will be summarized and free of PHI/PII. Reports will be made available through email to the study sites or via the Group PT SharePoint site (access limited to enrolled sites). *EnREP* begins with the same activities as foundational REP. After 6 months, sites randomized to enREP (n=8) that do not meet adoption benchmarks will receive 6 months of intensified implementation support. Adoption will be defined as delivery of Group PT as a clinical service (delivery of at least 1 Group PT class) and enrollment of at least 5 patients within a 6-month period. Patients must attend at least one Group PT class to count towards enrollment metrics. Additionally, sites randomized to enREP that met adoption benchmarks but do not meet the sustainment benchmark (defined as enrolling 15 new patients between months 7-9), will also receive intensified implementation support for the remainder of the study period. Higher intensity strategies will consist of calls between site implementation teams and a Function QUERI facilitator every 2-3 weeks to promote interactive problem solving in the context of a supportive interpersonal relationship. For the quantitative surveys that are completed twice by participating VA staff, (in the pre-implementation phase at baseline and post-implementation phase at 12 months) we will offer a raffle for small prizes (\$30-\$50) as an incentive to increase survey completion.

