Patient sample. Patients will be eligible for the Group PT if they have a clinician diagnosis of symptomatic knee OA. Participants will not be included if they have knee pain from another condition, have substantial fall risk, or have other co-occurring health conditions that would make participation in a group exercise class unsafe.

Outcomes. Implementation Outcomes: Implementation adoption will be defined as delivery of Group PT as a clinical service (delivery of at least 1 Group PT class) and enrollment of at least 5 patients within a 6-month period. Patients must attend at least one Group PT class to count towards enrollment metrics. **Penetration** (primary implementation outcome) will be defined as the average number of patients enrolling in the EBP on a monthly basis. **Fidelity** will be defined as the average number of sessions attended by patients who enroll in the EBP. We will also assess the number of referrals to the program, along with the proportion of referrals that result in patients enrolling in the program and reasons for failure to enroll. These metrics will be assessed at 6 months and 12 months (primary) following the initiation of the implementation period.

Effectiveness Outcomes/Quality Metrics will be collected by the physical therapist (e.g., via pen and paper or VA approved survey platform such as VA Qualtrics Research) and documented as health factors in the EHR (within a standardized clinic note template developed by the Function QUERI team), during every group PT class (six total). (*Note: Qualtrics is commercially available and the only approved instance for VA use is the VA Qualtrics Research listed in the ATO.*) These patient-level measures focus on functional outcomes and experience of care, in alignment with the CMS Meaningful Measures Framework, including the Patient-Reported Outcomes Measurement Information System (PROMIS), 30-second chair stand,

maximum pain during the chair stand test on a numeric rating scale (0-10) and patient satisfaction.⁷²⁻⁷⁴ We will continue to track patient outcomes beyond the 12-month formal engagement with enrolled sites to monitor continued progress with Group PT delivery. We may also generate additional data reports for sites to support program sustainment. As outlined above (Group PT Implementation Activities), these reports will be free of PHI/PII and made available through email or via the Group PT SharePoint site (access limited).

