Analyses. To address the question: Are there differences in implementation outcomes (adoption, penetration, fidelity) at 6 and 12 months between arms? We hypothesize that sites randomized to enREP will have superior implementation outcomes, including higher adoption, penetration and fidelity, compared with foundational REP sites at 12-months. We will use generalized linear models⁷⁵ to examine the effect of foundational vs. enREP on implementation outcomes at 12-months. The main predictors of interest will be Foundational REP vs. enREP and stratification variables for the Complexity Level, where sites 1a, 1b, and 1c are one category and all others (2, 3, CBOCs/ Health Care Centers) are the other category (bottom guartile vs. higher) and Rurality, where sites serving ≥50% rural/highly rural Veterans are one category and sites serving <50% rural/highly rural Veterans are another category. We will examine how implementation outcomes change over time using descriptive methods (e.g. plots, descriptive statistics, subgroups). To address the question: What are effectiveness outcomes (function, pain) at implementing sites? We will describe effectiveness/quality outcomes for patients who enroll in the Group PT program, overall and by study arm. We will calculate descriptive statistics for all visits, and change outcomes, among patients who have data from the first and last visits. Qualitative data collection and approaches to data integration are described previously.

Sample size estimate. Sample size calculations were conducted for the implementation outcomes at 12-months. Using a two-sided t-test based on a sample size of 16 sites (8 foundational REP and 8 enREP), a type-1 error rate of 5%, we will have 80% power to detect an effect size difference of 1.5 and 90% power to detect an effect size difference of 1.7 between arms. For the primary penetration outcome, assuming standard deviations ranging from 1.5 to 2.5 based on data of number of new patients per month over a 1-year period of implementation of Group PT in Durham, these effect size differences correspond to differences in mean number of initiators per month ranging from approximately 2.3 to 3.8 between arms for 80% power and 2.6 to 4.3 for 90% power.

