Analyses. To address the question: How should the STRIDE clinical program be adapted to optimize sustainability? We will use the FRAME to classify STRIDE adaptations at 17 VAMCs that have started programs (via VISN 6 rollout, ongoing Function QUERI trial or other means). Data sources will include study team notes, communications, interview transcripts, and data collected on Diffusion Network calls. Responses will be coded and analyzed at site levels to develop facility-level summaries of STRIDE adaptations, indicating where there is divergence in responses at the site-level. From this coded data, we will identify and visually display emergent themes in a matrix, with columns reflecting implementation outcomes (i.e., fidelity and penetration) arranged from high to low, to illustrate patterns in program adaptations according to implementation outcomes. To address the question: Are there differences in implementation outcomes (penetration, fidelity) at 10 months (primary), 13, 16 months between arms? We hypothesize that sites randomized to enREP will have higher penetration (proportion of eligible patients with ≥ 1 STRIDE documented walk during hospitalization) and fidelity (eligible hospitalizations with at least one documented STRIDE walk as the percentage of eligible hospital days with "full dose" of the program, defined as two or more documented walks or one for more than five minutes.). We will use generalized linear models⁷⁵ to examine the effect of foundational vs. enREP on implementation outcomes at 10-months. The main predictors of interest will be foundational REP vs. enREP and stratification variables used in the covariate constrained randomization (described above). We will examine how fidelity and penetration outcomes change over time using descriptive methods (e.g. plots, descriptive statistics, subgroups). To address the question: What is the impact on effectiveness outcomes and quality metrics (hospital length of stay or discharge to nursing home) at implementing sites? In exploratory analyses, we are interested in assessing the impact of STRIDE on hospital LOS, discharge to nursing home, and inpatient fall rates. Our sample of Veterans for this analysis will

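### Group PT's primary outcome has no stated averaging window, the model leaves out enrolment from the six months before support can differ, and the detectable difference rests on one site's monthly SD

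*Combined protocol and SAP*

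**What the plan says.** All references are to the combined protocol and SAP, mainly Implementation Project 1: Group PT for Knee OA.

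- **Outcome (Outcomes).** Penetration, the primary implementation outcome, "will be defined as the average number of patients enrolling in the EBP on a monthly basis". Timing: "These metrics will be assessed at 6 months and 12 months (primary) following the initiation of the implementation period". No sentence says which months enter the 12-month average.
- **Support by arm (Implementation activities).** EnREP "begins with the same activities as foundational REP". Then: "After 6 months, sites randomized to enREP (n=8) that do not meet adoption benchmarks will receive 6 months of intensified implementation support". EnREP sites that meet adoption but miss the sustainment benchmark (15 new patients in months 7-9) "will also receive intensified implementation support for the remainder of the study period". EnREP sites that meet both benchmarks are never intensified.
- **Model (Analyses, repeated under Data Analysis and Statistical Considerations).** A generalized linear model at 12 months. "The main predictors of interest will be Foundational REP vs. enREP and stratification variables for the Complexity Level", with rurality as the second stratification variable. Early enrolment is not a covariate.
- **Sample size (Sample size estimate, repeated under Data Analysis and Statistical Considerations).** A two-sided t-test at 5% on 8 versus 8 sites, with 80% power at 1.5 SD and 90% at 1.7 SD. These become 2.3-3.8 and 2.6-4.3 patients per month by assuming "standard deviations ranging from 1.5 to 2.5 based on data of number of new patients per month over a 1-year period" of Group PT in Durham.

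**The concern.** The two strategies differ only after the month-6 decision. A primary average that includes months 1-6 adds six months that cannot carry an effect of intensified support, and with 16 sites there is little power to spare. The same six months are a useful pre-divergence measure of how readily each site enrols, yet the model does not use them.

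The detectable difference has a separate problem. The test compares site averages, so the relevant SD is how much those averages vary between sites. The background section says Group PT had been implemented at one site. One site's monthly counts show variation within that site and cannot show variation between sites. At stake are the trial's ability to detect a useful enREP effect and the meaning of the difference it claims to be able to detect.

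**Working it through.** **1. The plan's own figures.** Noncentral t, 14 df, noncentrality d/√(1/8+1/8). Power is 79.7% at d = 1.5 and 88.5% at d = 1.7; exactly 80% needs d = 1.507. Differences: 1.5 × (1.5, 2.5) = 2.25, 3.75, and 1.7 × (1.5, 2.5) = 2.55, 4.25. The stated figures reproduce on their own inputs.

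**2. What a 12-month window would do.** Let A and B be a site's mean monthly enrolment in months 1-6 and 7-12. The 12-month mean is (A+B)/2. An effect δ that appears only in B becomes δ/2. With s the SD of B, k the ratio SD(A)/SD(B), and r the correlation of A with B:

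- 12-month mean: SD = (s/2)√(1+k²+2rk), so d = (δ/s)/√(1+k²+2rk), 14 df.
- Months 7-12: d = δ/s, 14 df.
- Months 7-12 adjusted for A: d = (δ/s)/√(1−r²), 13 df. This does not depend on k.

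The df are before the stratification terms. Assumptions, not in the documents: δ/s = 1.507 at all eight enREP sites, immediate and constant from month 7; r from 0.3 to 0.8; k = 1 or 0.5.

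| Analysis | r = 0.3 | r = 0.5 | r = 0.8 |
|---|---|---|---|
| 12-month mean, k = 1 | 41% | 37% | 32% |
| 12-month mean, k = 0.5 | 62% | 56% | 50% |
| Months 7-12 | 80% | 80% | 80% |
| Months 7-12 adjusted for months 1-6 | 83% | 89.5% | >99% |

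For example, k = 1 and r = 0.3 give d = 1.507/√2.6 = 0.93. In a linear model, regressing (A+B)/2 on arm and A halves both the arm coefficient and the residual SD compared with regressing B on arm and A. The t-statistic is therefore the same, and the covariate recovers the loss whichever window is chosen.

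**3. Not every enREP site is intensified from month 7.** Over 12 months, a site intensified from month 7 keeps 6/12 of a constant effect. A site intensified from month 10 keeps 3/12, and one never intensified keeps none. As an illustration (assumption), take four sites from month 7, two from month 10 and two never. Months 7-12 keep (4×1 + 2×0.5)/8 = 62.5% of the effect, so d = 0.625 × 1.507 = 0.94 and power is 42%. Adjusting for months 1-6 raises this to 45% at r = 0.3, 52% at r = 0.5 and 83% at r = 0.8.

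**4. A check against the plan's benchmarks.** A site that misses adoption has enrolled at most 4 patients in six months, or 0.67 per month. Raising its 12-month average by 2.3 takes 2.3 × 12 = 27.6 extra patients, all in months 7-12, or 4.6 per month. The sustainment benchmark is 15/3 = 5 per month.

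**5. The SD.** Treating months as independent, the SD of a site's 12-month mean is √(between-site SD² + monthly SD²/12). Monthly SDs of 1.5-2.5 contribute only 1.5/√12 = 0.43 to 2.5/√12 = 0.72. The rest is between-site SD, which the documents do not give. The 80% detectable difference (1.5 × total SD) over assumed values is:

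| Between-site SD | Total SD, 12-month mean | Detectable difference per month |
|---|---|---|
| 1 | 1.09-1.23 | 1.6-1.9 |
| 2 | 2.05-2.13 | 3.1-3.2 |
| 3 | 3.03-3.09 | 4.6 |

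The stated 2.3-3.8 lies inside this spread.

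**The case against.** **The window.** A reader might infer that the plan averages over all 12 months. The documents do not say so. Adoption is defined over a 6-month period in the same paragraph, so consecutive half-year windows are a fair reading. Caregivers FIRST names its 12-month period explicitly where one is meant. The one-year period in the sample-size text describes the Durham data, not the outcome. This objection stands: the defect is an unstated window.

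**Halving.** A reader might also infer that any enREP effect is halved. One half is exact only if all eight sites are intensified from month 7 with an immediate, constant effect. With later or no intensification less remains, and some dilution persists in months 7-12.

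**The power loss.** It depends on the period SDs. Sites already running a knee OA group class are ineligible, so months 1-6 are start-up and may vary less. The k = 0.5 row reflects this, and the loss is then smaller but still material. The correlations have no source in the documents.

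**Estimand.** A whole-year average is a legitimate target for a stepped strategy, and leaving out a covariate does not bias a randomised comparison. Both points are right. The window is partly a choice of estimand, and the covariate is a matter of efficiency. The 6-month comparison between arms is not the confirmatory test, because the hypothesis and the models are set at 12 months.

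**The SD.** A reader might conclude that power is overstated. With no between-site SD, the direction of the error is unknown. The plan does label the SDs as assumed.

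**STRIDE.** Its model also omits early data, but its outcome is a proportion assessed at 10 months and nothing here was calculated for it. The point does not extend to STRIDE.

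**Conclusion.** The point holds for Group PT in three parts. The averaging window is unspecified and does not exclude six months of identical support. If it is months 1-12, at most half of a constant effect remains, and power for an effect of about 1.5 SD falls from 80% to about 32%-41% (equal period SDs) or 50%-62% (early SD half as large). Months 1-6 enrolment is unused, although adjusting for it would give 83% to over 99% under the same assumptions, or 45%-83% instead of 42% if 62.5% of the effect remains. All of these figures are conditional on an assumed effect, an assumed correlation of 0.3-0.8, and random assignment alone not changing early enrolment.

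The detectable differences of 2.3-3.8 and 2.6-4.3 per month are arithmetically correct but use the wrong variance component. They may be too high or too low. The documents support neither a fixed 12-month window, nor a universal halving, nor a claim of bias.

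**What to change.** 1. Add each site's months 1-6 mean monthly enrolment as a covariate beside complexity and rurality. Site enrolment is already tracked for the month-6 benchmark. The cost is one degree of freedom (14 to 13 before the stratification terms).
2. State the primary window. Mean monthly enrolment in months 7-12 at all 16 randomised sites, analysed as randomised, is preferable, with the 12-month average as secondary. If the team wants the whole-year average as its estimand, it should say so; in a linear model the covariate in item 1 then gives the same test.
3. Restate the detectable difference, in both the Group PT section and Data Analysis and Statistical Considerations, in between-site SD units for the chosen window. Give a labelled range of assumed between-site SDs and stop presenting the Durham monthly SD as the basis.

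Items 2 and 3 are wording changes and need no new data. The restated detectable difference may look less favourable.

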Function QUERI's clinical programs were selected on the basis of alignment with national VA strategic goals, those of our operational and clinical partners, and potential impact for Veterans. The underlying clinical framework is the International Classification of Functioning. Disability and Health (ICF, Fig. 1). An individual's functional status is dynamic, with stressors such as hospitalization or development of a symptomatic chronic illness being important tipping points into disability. 1 Each EBP directly addresses known stressors and/or contextual factors that influence functional ability and independence. Project 1 examines implementation and effectiveness of Group Physical Therapy (Group PT) for knee osteoarthritis (OA; health condition), a leading cause of pain and disability among VA healthcare users.2 Many of the negative effects of knee OA can be successfully mitigated through PT, a recommended core component of treatment;^{3,4} however, many VA healthcare users with knee OA do not receive PT, and a key barrier is the high demand for PT services in the VA. To address this gap in access, we previously conducted a randomized controlled trial (RCT) comparing group-based PT vs. traditional individual PT for knee OA. The Group PT program consisted of 6 sessions, led by a physical therapist, that focused on evidence-based, functional exercises for individuals with knee OA, along with individual tailoring and guidance on progression and delivery of specific didactic content (e.g., activity pacing and managing pain with exercise). Group PT resulted in equivalent or greater improvements in pain and functional outcomes compared with traditional PT, which is important because the group-based model provides care to more Veterans with fewer staffing resources, thereby increasing access and efficiency.⁵ Project 2 compares implementation strategies for large scale spread of STRIDE, a supervised walking program for hospitalized older Veterans. STRIDE focuses on maintaining musculoskeletal strength and mobility during hospitalization (environmental factor), a highly vulnerable time for development of disability. 6 STRIDE is designed for patients aged > 60 years and consists of a one-time gait and balance assessment conducted by a PT, followed by daily walks supervised by a mobility assistant for the duration of the hospital stay. Clinical demonstration of STRIDE conducted at the Durham VA resulted in a greater likelihood of discharge to home than to skilled nursing or rehabilitation among STRIDE participants compared to clinically similar patients receiving usual care (92 vs 74%, p = 0.007). Based on this experience, the cumulative evidence of the positive impact of early mobility interventions, 8-15 and successful spread to other hospitals, 16,17 STRIDE has the potential to become a system-wide approach to address hospital-associated disability in VA. Project 3 examines implementation of Caregivers FIRST (Caregivers Finding Important Resources, Support, and Training), an evidence-based skills training program for caregivers of Veterans with cognitive and/or functional limitations. Caregivers FIRST promotes Veteran function and independence through caregiver skill training and support (personal factors) in a series of 4 proactive group classes to help general caregivers build self-care and psychological coping, health system navigation, and hands-on clinical skills. The RCT of Caregivers FIRST

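### Group PT fidelity averages sessions over every patient with at least one class, with no time allowed for finishing the six, so late-enrolling sites can score lower for identical delivery

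*Combined protocol and SAP*

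**What the plan says.** All references are to the combined protocol and SAP, Implementation Project 1 (Group PT for Knee OA), unless stated.

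- **Course length.** Background and Significance: "The Group PT program consisted of 6 sessions, led by a physical therapist". The Outcomes paragraph also counts six classes.
- **Who counts.** Outcomes: "Patients must attend at least one Group PT class to count towards enrollment metrics".
- **Fidelity.** Outcomes: it "will be defined as the average number of sessions attended by patients who enroll in the EBP".
- **Timing.** Outcomes: "These metrics will be assessed at 6 months and 12 months (primary) following the initiation of the implementation period".
- **Intensified support.** Implementation activities: after month 6, "sites randomized to enREP (n=8) that do not meet adoption benchmarks will receive 6 months of intensified implementation support". Sites that adopted but enrol fewer than 15 new patients in months 7-9 get it for the rest of the study.
- **Hypothesis.** Analyses: enREP is expected to do better, "including higher adoption, penetration and fidelity, compared with foundational REP sites at 12-months".
- **After month 12.** Outcomes: "We will continue to track patient outcomes beyond the 12-month formal engagement with enrolled sites". This is not linked to fidelity.

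The plan does not state how far apart classes are, whether sessions after the assessment date count for patients already enrolled, or whether the 12-month value is cumulative or covers months 7-12. The repeated analysis text under Data Analysis and Statistical Considerations does not settle these points.

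**The concern.** A patient whose first class falls just before the assessment date enters the average with one or two sessions, whatever the quality of delivery. The more of a site's enrolment lies close to that date, the lower its score. Intensified support begins after month 6, so any enrolment it generates comes late, and fidelity is one of the outcomes that enREP is meant to raise. A result of more patients but fewer sessions each could then come from incomplete follow-up alone.

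The plan allows for opportunity elsewhere. STRIDE fidelity is a percentage of eligible hospital days, which puts the time available in the denominator. Group PT change scores use only patients with first-visit and last-visit data. Group PT fidelity has no such protection. The Caregivers FIRST counterpart counts classes per caregiver over a 12-month period. That does not decide the Group PT rule, but it shows that a period-limited count is a natural reading.

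**Working it through.** **The plan's own figure.** The Sample size estimate gives 80% power at an effect size of 1.5 and 90% at 1.7 (8 vs 8 sites, two-sided 5%). The noncentral t with 14 degrees of freedom gives 79.7% and 88.5%, so the statement reproduces to within rounding. The only SDs given (1.5 to 2.5) are for patients per month, that is, for penetration. None is given for fidelity.

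**Inputs.** From the documents: six classes, enrolled after one, assessment at month 12. Assumed, because the documents are silent: equally spaced classes g weeks apart, perfect attendance, even enrolment over the last W weeks before the cut, and sessions after the cut not counted.

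**Formula.** With weekly classes, patients starting in the last five weeks lose 5, 4, 3, 2 and 1 sessions, 15 in all. For spacing g the total is 15g, so for W of at least 5g:

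site mean = 6 − 15g / W

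| Spacing (assumed) | Starts that cannot reach six | Even over 12 months (W = 52) | Months 7-12 only (W = 26) | Gap (unrounded inputs) |
|---|---|---|---|---|
| Twice weekly, g = 0.5 | last 2.5 weeks | 6 − 7.5/52 = 5.86 | 6 − 7.5/26 = 5.71 | 0.14 |
| Weekly, g = 1 | last 5 weeks | 6 − 15/52 = 5.71 | 6 − 15/26 = 5.42 | 0.29 |
| Every two weeks, g = 2 | last 10 weeks | 6 − 30/52 = 5.42 | 6 − 30/26 = 4.85 | 0.58 |

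If each of classes 2 to 6 is attended with probability 0.7, the true value is 1 + 5 × 0.7 = 4.5 and each loss is multiplied by 0.7. Weekly classes then give 4.30 and 4.10.

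**6-month summary.** If the counts are cumulative, a site enrolling evenly from the start with weekly classes reads 6 − 15/26 = 5.42 at month 6 and 5.71 at month 12, an apparent improvement with no change in delivery.

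**Between arms.** Assume no true difference, weekly classes, and four of eight sites per arm not adopting by month 6. Adopters start after 3 months (W = 39): 6 − 15/39 = 5.62. The enREP non-adopters start after 9 months (W = 13): 6 − 15/13 = 4.85. The enREP mean is (4 × 5.62 + 4 × 4.85)/8 = 5.23. The result depends on what the REP non-adopters do:

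- They never start and drop out of the average: REP mean 5.62, difference **−0.38** (−0.19 twice weekly, −0.77 every two weeks).
- They start at the same time as the enREP non-adopters: difference **0**.
- They start after 11 months, with 4.33 weeks left: those sites score (1 + 2 + 3 + 4 + 5 × 0.33)/4.33 = 2.69, the REP mean is 4.15, and the difference is **+1.08** (+0.58 twice weekly, +1.04 every two weeks).

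**Check of the remedy.** At the longest spacing tried, the sixth class comes 5 × 2 = 10 weeks after the first. With three months of extra capture, the mean returns to 6.00 for starts at months 3, 9 and 11 at all three spacings.

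**The case against.** The strongest reply is that the plan says when fidelity is assessed, not that later sessions are discarded, and that it foresees tracking past month 12. This is right: the cut-off is implied, not stated. But the tracking sentence is not tied to fidelity, and two analysts could compute different values from the present text.

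Three stronger readings are tempting and are not supported:

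- *The comparison is biased against enREP.* A reader might infer this from the timing of intensified support. Truncation affects late-enrolling sites in both arms, and foundational REP continues after month 6, so REP non-adopters can also start late. The sign depends on which arm enrols later.
- *Patients who start in months 7-12 cannot finish.* Only those in roughly the last 2.5 to 10 weeks are affected, depending on spacing. With weekly classes and even enrolment over months 7-12, that is 5/26, or 19%.
- *Sites given support for missing the sustainment benchmark could enrol only in the last quarter* (mean 4.85 weekly, 3.69 every two weeks). They cannot, because they must already have enrolled at least five patients to meet adoption. Those figures fit only a non-adopting site with nobody enrolled before month 10.

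It is also fair to say that fidelity is not the primary outcome and that, without an SD, a loss in sessions cannot be expressed as power or effect size. The same truncation may touch the proportion of referrals that lead to enrolment, but the documents give no lag from referral to first class, so no size can be put on it.

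**Conclusion.** The concern holds in a conditional form. The definition lets patients without time to finish into the average. If sessions stop counting at the assessment date, two sites with identical delivery differ by 0.14 to 0.58 of six sessions when one enrols evenly over the year and the other only in months 7-12. This rests on perfect attendance, even enrolment within each period, and spacing between twice weekly and every two weeks.

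The arm-level effect can be negative, nil or positive. In the illustration with weekly classes it is −0.38, 0 or +1.08 sessions, according to when, or whether, the REP non-adopters start. The effect on power cannot be stated. Penetration is unaffected. The definition should be changed before fidelity is analysed, because a better one is available from attendance already in the EHR.

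**What to change.** 1. Define Group PT fidelity as the number of sessions attended within a fixed period from each patient's first class, long enough to cover all six classes on the site's schedule. Include every patient whose first class falls in the outcome window, and read EHR attendance past the assessment date where needed.
2. Say whether the 12-month window is cumulative or covers months 7-12, and apply the same per-patient rule at 6 months.
3. State how sites with no enrolled patients enter the fidelity analysis, and report how many sites contribute in each arm. The per-patient window alone does not settle this, and the −0.38 case arises when such REP sites drop out.
4. Optionally, use a fixed period from referral for the proportion enrolling.

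**Cost.** This is a change of outcome wording. The fidelity readout waits for the length of the window (about 12 weeks would cover the longest spacing tried here), and some attendance after the 12-month engagement is counted. The penetration readout is not delayed.

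**Alternative, if post-engagement attendance is not wanted.** Limit the average to patients who started early enough to complete. There is no delay, but the newest patients are lost: with weekly classes, 5/52 = 10% at an evenly enrolling site and 5/26 = 19% at one enrolling only in months 7-12. A site starting within the last five weeks would contribute nobody.
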